5.2.1.5 Sensitivity Analyses

The following sensitivity analyses will be performed:

1. If there are patients with missing baseline ATRS, a sensitivity analysis will be conducted in the patients that has baseline a measurement (i.e. excluding the patients with missing baseline measurement).
2. If the missing baseline ATRS measurements were imputed using median imputation (see Section 5.2.1.4), a sensitivity analysis will be conducted using mean imputation instead.
3. The ATRS questionnaire is known to sometimes be misinterpreted, and inverted, by patients (10, 11). If the study group suspects that this has happened for one or more patients at any time point, a sensitivity analysis will be conducted where these possibly inverted ATRS measurements are inverted back. I.e. if a patient e.g. has answered the value 2 on an item in the questionnaire, this is converted to $10-2=8$. This is only done for patients where the study group suspects that the scale has been inverted.
4. A sensitivity analysis will be conducted in the PPS, the per protocol set. That is, if any patients received a different treatment than randomized to, they will in this sensitivity analysis be placed in the treatment group corresponding to the treatment they actually received.
5. A sensitivity analysis will be conducted in patients that has complete follow-up ATRS measurements, the complete case set (CCS).

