2.1 Trial Design

The Achilles study is designed as a randomized, controlled, multicentre, single-country, comparative study.

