2.2 Randomisation

Eligible patients were allocated in a 1:1:1 ratio between CT, OR and MIS. Treatment allocation was done by block randomization, stratified by hospital, with 6, 9 or 12 patients in each block. Details of allocation sequence generation was provided in a separate document unavailable to those who enrolled patients or assigned treatment.

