2.3 Sample size

The sample size was based on the primary endpoint of ATRS at 1-2 years. The calculation was based on a one-way ANOVA analysis, assuming a standard deviation of 20 in each treatment group. A total sample size (study completers) of 480 (160 in each group) was deemed necessary to achieve 80%

STATISTICAL ANALYSIS PLAN for the Achilles trial

power to detect a difference of ATRS of 7 between the groups in two-sided tests at 5% significance level. To compensate for withdrawals/loss to follow-up, a total enrolment of 530 patients was targeted.

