5.1.1.2 Achilles tendon Total Rupture Score

The acute Achilles tendon Total Rupture Score (ATRS) was developed in Sweden and published in 2007 (2). The ATRS is a patient reported outcome measure (PROM) designed to assess outcomes in patients with ruptures of the Achilles tendon. It contains ten questions, and each question is answered on an 11-point Likert scale ranging from 0 to 10. The total score is calculated by summing the individual Likert items. A score of 100 represents the absence of symptoms, whereas a score of 0 represents severe symptoms. The Norwegian version of the ATRS was validated, reliability tested and published in 2017/2018 (3). The Norwegian adaption of the ATRS demonstrates acceptable validity and reliability for use in the Norwegian population to assess clinical outcomes in patients with Achilles tendon ruptures.

If any of the 10 questions lacks an answer, this trial will follow the ATRS manual (8). Most importantly, if one or more of the 10 questions lacks an answer, the total ATRS score is treated as a missing value.

5.1.1.3 Short Form 36

STATISTICAL ANALYSIS PLAN for the Achilles trial

The Short Form 36 (SF-36) is a self-assessment health status questionnaire composed of 36 questions sorted into eight multi-item scales. The SF-36 also provides two summarized measures represented by the physical component summary (PCS) and the mental component summary (MCS). The validity and reliability of the Norwegian translation of SF-36 have been found to be satisfactory (4, 5).

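### The SAP re-inverts ATRS questionnaires on the study group's suspicion, with no stated criterion, timing or masking, which weakens this sensitivity analysis as a check on inverted scores

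*SAP*

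**What the plan says.** SAP section 5.2.1.5, item 3, recognises that patients sometimes misread the ATRS and answer it the wrong way round. The trigger for acting is: "If the study group suspects that this has happened for one or more patients at any time point". In that case "a sensitivity analysis will be conducted where these possibly inverted ATRS measurements are inverted back", with each item value x replaced by 10 - x. The item closes by limiting who is affected: "This is only done for patients where the study group suspects that the scale has been inverted".

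The direction of the scale is set in section 5.1.1.2: "A score of 100 represents the absence of symptoms, whereas a score of 0 represents severe symptoms". Sections 5.1.1.2 and 5.2.1.4 refer to the ATRS manual for unanswered items and item values. Neither says that the manual supplies a rule for detecting inversion.

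On design, section 2.1 says: "The Achilles study is designed as a randomized, controlled, multicentre, single-country, comparative study". Section 2.2 keeps the allocation sequence from those enrolling patients or assigning treatment. That is concealment at entry, not masking of later data review. The SAP does not mention blinding or masking anywhere.

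**The concern.** Inversion can only be suspected by looking at the outcome: a total that seems too low, or out of line with the patient's other data. If the person judging also knows the arm, the same score may look plausible in one arm and mistaken in another. The arms are open surgery, minimally invasive surgery and conservative treatment, and section 5.1.3.2 has re-ruptures reported continuously to the principal investigator. Nothing in the SAP separates knowledge of arm from the judgement on scores.

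Even without any leaning, two people following item 3 faithfully could reverse different patients. The SAP sets numerical triggers for other contingent steps: the 5% threshold for patients without follow-up (5.2.1.4), expected counts below 5 (5.2.2.1), and the 1% trimming and 10th-percentile bound for failed tests (5.2.4.4). Item 3 has no equivalent.

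What is at stake is the value of this check. It is the only analysis in the SAP aimed at a measurement error that the SAP itself calls known. If reversals may depend on arm, neither agreement nor disagreement with the primary result can be read with full confidence.

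**Working it through.** **Inputs from the SAP.** Section 2.2: "Eligible patients were allocated in a 1:1:1 ratio between CT, OR and MIS". Section 2.3: "assuming a standard deviation of 20 in each treatment group", and "A total sample size (study completers) of 480 (160 in each group) was deemed necessary to achieve 80" per cent power for a difference of 7 ATRS points, two-sided 5%.

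**Reproducing the plan's figure.** Take a one-way ANOVA with three groups, SD 20 and means spread evenly over the 7-point range (0, 3.5, 7). The noncentral F distribution then needs 159 per arm (477 in total) for 80% power, and 160 per arm gives 80.4%. The SAP's 480 is reproduced, so 160 per arm and SD 20 are a fair scale for what follows.

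**Size of one reversal.** Replacing each of ten items x by 10 - x turns a total S into 100 - S, a shift of 100 - 2S. For one patient in an arm of 160, the arm mean moves by (100 - 2S)/160.

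**Benchmark.** The unadjusted pairwise difference that just reaches two-sided 5% is 1.96 × 20 × √(2/160) = 1.96 × 2.236 = 4.38 points.

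**Range over assumed raw scores.** The values of S and the numbers of reversals are assumptions; the SAP gives neither. Only the net excess in one arm counts.

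| Raw total S at 1-2 years | Shift for that patient | Shift in arm mean per net reversal | Net one-sided reversals to create 4.38 from zero | Same, as share of 160 |
|---|---|---|---|---|
| 10 | 80 | 80/160 = 0.50 | 4.38/0.50, so 9 | 5.6% |
| 20 | 60 | 60/160 = 0.375 | 4.38/0.375, so 12 | 7.5% |
| 30 | 40 | 40/160 = 0.25 | 4.38/0.25, so 18 | 11.3% |

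**Effect within the sensitivity analysis.** With S = 20 and no true difference, 4 net extra reversals in one arm shift its mean by 4 × 0.375 = 1.5 points. The omnibus rejection rate in that analysis rises from 5% to about 10%. With 8 net reversals (3.0 points) it rises to about 26%.

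**Limits of the arithmetic.** These are unadjusted ANOVA approximations with the SD held at 20, not results from the SAP's mixed model. They cover reversals at 1-2 years only, although item 3 allows them at any time point.

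**The case against.** The strongest reply is that nothing confirmatory depends on item 3. The primary analysis in section 5.2.1.1 makes no use of reversed scores, and the testing procedure and decision rule (2.4.1 and 2.4.2) rest on that analysis alone. Keeping doubtful corrections out of the primary analysis is the cautious choice. This stands in full. A reader might infer that the plan edits the primary outcome without masking; the SAP does not support that, because reversed scores enter one of five sensitivity analyses and the unaltered result stands beside it.

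Second, silence on masking is not evidence that masking was absent. The protocol is not shown and may say who reviews the data and what they can see. This also stands: the supportable statement is that the SAP does not state that the decision is masked.

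Third, no arm is favoured in the SAP; its objective and tests are symmetric and two-sided. Knowledge of arm would permit differential reversal but does not show that it happens, and a sizeable net imbalance is needed before this analysis reaches significance from zero. This stands as a limit on severity. It does not remove the gap, because a selection based on the outcome value needs a fixed criterion, masking or both, and the SAP states neither.

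**Conclusion.** The point holds as a weakness of one sensitivity analysis. Section 5.2.1.5, item 3, leaves the selection of patients to suspicion, without a criterion, a time or stated masking. Followed as written, it allows arm-dependent reversals and is not reproducible.

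A few net reversals at low raw scores would move an arm mean by about 1 to 2 points, and roughly 9 to 18 net one-sided reversals would be needed to create a just-significant pairwise difference. Those figures rest on 160 per arm, SD 20 and assumed raw totals of 10 to 30. It would go too far to conclude that the analysis is biased or without value: differential reversal is possible, not demonstrated. Severity is low to moderate.

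**What to change.** Replace suspicion in item 3 with a written criterion that does not refer to treatment arm, and apply it to every patient at every visit. Those applying it should work from a listing without allocation and finish before the database lock described in section 2.6. State in the SAP who they are, and report the number flagged by arm and visit.

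One possible criterion is that 100 minus the ATRS total agrees better with adjacent visits than the recorded total does, by a margin fixed in advance. Same-visit SF-36 physical function could support it where collected: baseline, 6 months and 1-2 years (section 5.1.3.1). It is not collected at 3 months, so that visit must rely on the adjacent ATRS scores. Because physical function is itself a compared secondary outcome, it should support the flag rather than decide it alone.

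The cost is a paragraph of SAP wording and one masked listing; no new data are needed. The downside is that a fixed criterion may miss some true inversions and flag some genuine low scores, particularly where recovery between visits is large. It would do so equally across arms for the same pattern of scores.

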5.2.1.6 Subgroup Analyses

No subgroup analyses will be performed.

5.2.2 Dichotomous Secondary Outcome: Re-ruptures

5.2.2.1 Main Analysis

The probability of re-rupture will be compared pairwise between the three treatment groups.

A logistic regression model will be fitted to the data, where the treatment variable will be adjusted by study centre (the stratification factor used in the randomization). From the model, the estimated marginal means of the risk difference between the groups will be reported pairwise.

We expect that the number of re-ruptures will be low, which may lead to the normality approximation to the binomial distribution becoming questionable. If any of the expected numbers in one of the cells in the 3-by-2 contingency table, summarizing the number re-ruptures in the treatment groups, is less than 5, the following analysis will be performed in place of fitting the logistic regression model: The confidence intervals of the risk difference between the groups will pairwise be calculated using the Newcombe Hybrid Score[12]. Thus, the risk difference will not be adjusted for study centre.

The analysis will be conducted in the FAS.

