5.2.2.3 Assumption Checks

A check of the expected numbers in the 3-by-2 Contingency table (see Section 5.2.2.1) will be done. If any of these numbers are less than 5, the non-parametric Newcombe Hybrid Score will be used to calculate the risk differences between the groups pairwise

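### The rule for keeping the centre-adjusted logistic model for re-rupture checks neither empty arms nor empty hospitals, and the SAP does not fix how its risk differences are averaged over hospitals

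*SAP*

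**What the plan says.** SAP 5.2.2.1 makes a logistic model the main analysis: "A logistic regression model will be fitted to the data, where the treatment variable will be adjusted by study centre". The result is a set of pairwise risk differences: "From the model, the estimated marginal means of the risk difference between the groups will be reported pairwise". The SAP does not say whether the averaging over centres is done on the logit or the risk scale, with what centre weights, or how the interval is formed.

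The section anticipates sparse data ("We expect that the number of re-ruptures will be low") and sets one condition for leaving the model: "If any of the expected numbers in one of the cells in the 3-by-2 contingency table" ... "is less than 5, the following analysis will be performed in place of fitting the logistic regression model". The fallback is unadjusted for centre: "The confidence intervals of the risk difference between the groups will pairwise be calculated using the Newcombe Hybrid Score". Section 5.2.2.3 repeats the condition as the only assumption check: "A check of the expected numbers in the 3-by-2 Contingency table (see Section 5.2.2.1) will be done". Section 5.2.2.5 plans no sensitivity analysis. Section 5.2.2.2 does require the arm-by-outcome table to be shown.

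**The concern.** The switch is there to catch data too sparse for the model. An expected count in an arm-by-outcome table depends only on the total number of events and the arm sizes. It does not show how the events fell between arms, although every reported contrast is pairwise. It cannot see hospitals at all, although the model has a term for each one.

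An arm or hospital without events has no finite coefficient (separation). The rule can therefore keep the model where its standard errors are unusable. Because the averaging scale is open, one data set can also give quite different risk differences under the same plan. Re-rupture is a listed secondary outcome, and it is where the SAP's background section says open repair may have an advantage.

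**Working it through.** **Inputs from the SAP.** Allocation: "Eligible patients were allocated in a 1:1:1 ratio between CT, OR and MIS" (2.2). Completers 480, or 160 per arm; enrolment target 530, or 530/3 = 176.7 per arm (2.3). Threshold: expected count below 5 (5.2.2.1). The SAP states no re-rupture rate, number of hospitals or hospital sizes, and it has no figure of its own on this point to reproduce.

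**Assumptions.** 177 per arm; four hospitals with 71/53/35/18 patients per arm (about 40/30/20/10%); events split over hospitals as shown.

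**Step 1: what the rule tests.** Smallest expected event count = total events × smallest arm / total patients.
- Equal arms: 15 × 1/3 = 5.00, so the model is kept from 15 events.
- Arms 176/177/177: 15 × 176/530 = 4.98, so from 16.
- Arms 160/175/185: 16 × 160/520 = 4.92, so from 17.

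With equal arms, 5/5/5, 12/3/0 and 15/0/0 all pass alike.

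**Step 2: one empty arm (12/3/0).** The fitted risk in the empty arm is practically zero, and so is its standard error. For 3 v 0 the size-weighted model interval is then that of the other arm alone:
- p = 3/177 = 1.69%; SE = √(0.0169 × 0.9831/177) = 0.97 points; 1.69 ± 1.96 × 0.97 = -0.2 to 3.6 points.
- Newcombe on the same counts: -0.7 to 4.9 points.

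**Step 3: two empty arms (15/0/0).** The interval between the two empty arms is 0.0 to 0.0 on every averaging scale. Newcombe gives -2.1 to 2.1 points.

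**Step 4: one empty hospital.** Events 11/2/3, split over hospitals as 5,3,3,0 / 1,1,0,0 / 1,1,1,0. The expected count is 16/3 = 5.33, so the model is kept. First arm minus second arm:

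| Averaging over hospitals | Difference (points) | 95% interval |
|---|---|---|
| Logit scale | about 0.03 to 0.1 | beyond ±100 |
| Risks, equal weights | 4.3 | 1.0 to 7.7 |
| Risks, weighted by hospital size | 5.1 | 1.2 to 9.0 |

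The crude difference is (11 - 2)/177 = 5.1 points. The logit-scale figure depends only on where the iterations stop, because its limit is zero.

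A second layout gives the same picture: 160 per arm, four equal hospitals, 9/3/3 events, one hospital empty. Logit averaging gives 0.07 (-54.8 to 55.0); risk averaging gives 3.75 (-0.36 to 7.86).

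**Step 5: how often.** Simulated trials that keep the model (at least 15 events):

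| Assumed risks | At least one empty arm | Two empty arms | At least one empty hospital |
|---|---|---|---|
| 8/1/1% | 26% | under 2% | 14% |
| 5/2/2% | 2% | below 0.01% | 16% |

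With 8/1/1% and a smallest hospital of 5% instead of 10%, an empty hospital occurs in about 39%. Given exactly 15 events, its probability runs from 5% (four equal hospitals) to 75% (eight equal hospitals).

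**The case against.** The plan foresaw few events, named a sound fallback and requires the 3-by-2 table to be shown, so empty arms would be in plain view. Re-rupture is secondary, and section 2.4.1 classes every test outside the ATRS hierarchy as supportive or exploratory. The SAP speaks of marginal means of the risk difference, which fits averaging of risks at least as well as averaging of logits. In the 11/2/3 example both risk-scale versions exclude zero, and the interval of the logit version is so wide that an analyst would notice. Average coverage of the size-weighted model interval was about 96% in simulation. All frequencies rest on assumed inputs.

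Most of this stands, and it limits the point. A reader might infer that any empty arm collapses the difference or gives a zero-width interval. It does not: one empty arm only narrows the interval, and zero width from empty arms needs two of them. A reader might also take 26% as a failure rate, but it counts trials with at least one empty arm. Nor does an empty hospital always spoil the result, since size-weighted risks are unaffected. The gap between 4.3 and 5.1 points is a choice of hospital weights, not a breakdown.

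Two parts of the objection do not hold. The 3-by-2 table does not show an empty hospital. A failed fit is also not always conspicuous: with 9/3/3 events at 160 per arm and two small empty hospitals (hospital sizes 70/60/22/8 per arm), logit averaging gives 0.001 points with an interval of -1.8 to 1.8, against 3.75 (-0.37 to 7.87) for size-weighted risks.

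**Conclusion.** The point holds in a limited form. The switch is in effect a threshold on total events, about 15 to 17 depending on arm balance, and nothing else in the SAP guards against separation.

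- **Empty hospital:** harmful if logits are averaged, which the SAP leaves open. The difference then goes towards zero with an interval that carries no information. Harmless if risks are averaged over the observed hospital mix.
- **One empty arm:** its uncertainty is dropped, so intervals involving it are too narrow (3 v 0: -0.2 to 3.6 against -0.7 to 4.9 points at 177 per arm).
- **Two empty arms:** zero-width interval between them, in under 2% of retained trials even at 8/1/1%.

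The threshold follows from the SAP's rule and the arm sizes. The frequencies depend on assumed risks and hospital sizes. The documents do not support a claim that the logistic analysis performs badly on average, or that the whole method must be replaced. The gap is worth closing before analysis because doing so is cheap and the SAP itself expects few events.

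**What to change.** In 5.2.2.1, state that risk differences from the logistic model are obtained by averaging predicted risks over the observed hospital mix, not by averaging logits. In 5.2.2.1 and 5.2.2.3, extend the switch: use the already planned Newcombe interval for any pair in which an arm has no observed re-rupture, as well as when an expected count is below 5.

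Using Newcombe for all pairs, or a hospital-stratified score interval for all pairs, is an acceptable alternative but goes further than the defect requires.

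The cost is a few sentences in the SAP and a few lines of code. The downside is that the centre adjustment is lost for the affected pairs, as it already is under the existing fallback.

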2.4 Statistical Framework

2.4.1 Hypothesis Test

This trial will employ a hierarchical testing procedure as follows:

1. First, a test of overall effect of treatment at 1-2 years is performed. The null hypothesis is that there is no difference in the change in ATRS score from baseline to 1-2 years between the three study arms. The alternative hypothesis is that there is a difference between at least two of the three treatment arms. The test will be performed at the (two sided) 5% significance level.
2. If the overall test shows that there is a significant difference on the 5% level, then tests of a difference in the change from baseline to 1-2 years ATRS score will be performed pairwise between the treatment arms. The null hypotheses in these tests will be that there is no difference between the treatment arms. The alternative hypotheses are that there is a difference between the two treatment arms being compared. These tests will be performed at the (two sided) 5% significance level.

The hierarchical testing procedure abides by the closed testing procedure, allowing a 5% significance level to be used in each test, while at the same time maintaining a family-wise error rate at 5%.

All other tests than described in step 1 and 2 above, will be regarded as supportive or exploratory.

Note that if the test in step 1 shows that there is no significant difference between treatment groups, a pairwise comparison between treatment groups will still be reported, but these are to be considered as secondary analyses.

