3.3 Analysis Populations

We define the following patient population in this trial.

- **All randomized patients:** All patients that have been randomized regardless if they actually received treatment or not.
- **Full analysis set (FAS):** All patients that are randomized, received treatment, and where ATRS was measured at least once post baseline (i.e. at 3 months, 6 months or 1-2 years). Patients are allocated to the treatment they were randomized to.
- **Per protocol set (PPS):** Similar to the FAS, but patients are allocated to the treatment they actually received.
- **Complete Case set (CCS):** The subset of patients in the FAS that has ATRS measurements at all follow-up visits. Patients are allocated to the treatment they were randomized to.

The FAS will be used for the primary analysis, while the PPS and the CCS will be used for sensitivity analyses.

4 Trial Population

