5.1.3.2 Re-rupture

Re-rupture is here defined as a total rupture of the same Achilles tendon as treated in the trial within the 12-month visit. Re-rupture will be treated as a dichotomous outcome. The diagnosis is done clinically without any need of imaging techniques. Re-ruptures were continuously reported to the principal investigator of the study. Patients suffering from either a re-rupture of the same Achilles tendon or a new rupture of the contralateral Achilles tendon were excluded from further testing and questionnaires.

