5.2.2.4 Missing Data

All patients are followed-up for re-ruptures until 12 months. The participating hospitals are instructed to report any re-rupture (total or partial) detected during the follow up period directly to the principal investigator. This will secure that the chance of missing the count of any re-rupture is regarded as insignificant.

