5.2.2.5 Sensitivity Analyses

No sensitivity analyses will be performed.

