6.1 Adverse Events

Any complications and adverse events were continuously documented and any new rupture on the injured side (re-rupture) or the healthy side were immediately reported to the study coordinator. Re-ruptures are considered as a secondary outcome (see Section 5.1.3.2). Adverse events other than re-ruptures will be tabulated.

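### Re-rupture is analysed in a set that patients who re-rupture early cannot enter

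*SAP*

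**What the plan says.** Three rules in the SAP bear on this.

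- Section 5.2.2.1, on the re-rupture comparison: "The analysis will be conducted in the FAS".
- Section 3.3 defines the FAS as: "All patients that are randomized, received treatment, and where ATRS was measured at least once post baseline". The eligible measurements are those at 3 months, 6 months and 1-2 years. Section 2.7 sets the first of these windows at days 61 to 121.
- Section 5.1.3.2 says that patients with a "re-rupture of the same Achilles tendon or a new rupture of the contralateral Achilles tendon were excluded from further testing and questionnaires".

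Section 5.2.2.4 states that all patients are followed for re-rupture until 12 months and that hospitals report directly to the principal investigator. It concludes: "This will secure that the chance of missing the count of any re-rupture is regarded as insignificant". Section 5.2.2.5 adds "No sensitivity analyses will be performed", and section 6.1 says "Adverse events other than re-ruptures will be tabulated".

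**The concern.** The FAS suits the ATRS, where at least one follow-up score is needed to contribute to the model. Re-rupture needs no questionnaire. Applied to re-rupture, the ATRS condition removes patients because they had the event early, so an arm's early re-ruptures are left out of its estimated risk.

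Re-rupture is a listed secondary objective (section 1.2.2), and the background (section 1.1) names a lower re-rupture risk as a possible advantage of open repair. It is therefore one of the comparisons readers will look for, and it would be biased by an amount and in a direction that the SAP does not allow one to work out.

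**Working it through.** **Who is lost.** Following the three rules for a patient who re-ruptures:

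1. Before day 61: no post-baseline ATRS window has opened, and no questionnaire follows. The patient never enters the FAS.
2. Within days 61 to 121 but before the patient's own 3-month form: same result.
3. Later, where the 3-month form (and the 6-month form, if already due) was missed or incomplete: same result. Under section 5.1.1.2 a single unanswered item makes the score missing.
4. After a valid post-baseline ATRS: the patient is in the FAS and the event counts.

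**Whether anything restores the events.** The multiple imputation in section 5.2.1.4 concerns the 1-2 year ATRS only. The 3-by-2 table in section 5.2.2.2 is the one from the same analysis. There is no sensitivity analysis, and the adverse-event table omits re-ruptures. The CONSORT diagram (section 4.1) would show the patients as excluded from the primary analysis, with reasons, but it does not change the estimated risks.

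**Size.** The SAP states no re-rupture figure to reproduce; section 5.2.2.1 says only that the number is expected to be low. The risks and early shares below are therefore assumptions. Let *r* be an arm's true 12-month risk and *s* the share of its re-ruptures that occur before the patient's first post-baseline ATRS. These patients leave numerator and denominator, so

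FAS risk = r(1 − s) / (1 − r·s).

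Example with r = 6%, s = 0.3: 0.06 × 0.7 / (1 − 0.018) = 0.042 / 0.982 = 4.28%. With r = 2%: 0.014 / 0.994 = 1.41%. Difference: 2.87 points, against a true 4.0.

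| True risks | Early share, arm A / arm B | FAS risk A | FAS risk B | Difference (points) |
|---|---|---|---|---|
| 6% / 2% | 0.1 / 0.1 | 5.43% | 1.80% | 3.63 |
| 6% / 2% | 0.3 / 0.3 | 4.28% | 1.41% | 2.87 |
| 6% / 2% | 0.5 / 0.5 | 3.09% | 1.01% | 2.08 |
| 6% / 2% | 0.7 / 0.7 | 1.88% | 0.61% | 1.27 |
| 6% / 2% | 0.2 / 0.8 | 4.86% | 0.41% | 4.45 |
| 6% / 2% | 0.8 / 0.2 | 1.26% | 1.61% | −0.35 |
| 5% / 5% | 0.3 / 0.5 | 3.55% | 2.56% | 0.99 |

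In counts: the enrolment target of 530 (section 2.3) gives 530 / 3 = 176.7 patients per arm. At 6% that is 10.6 events, of which 1.1, 3.2, 5.3 or 7.4 are lost at s = 0.1, 0.3, 0.5 or 0.7.

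**Other loss.** The formula takes every event-free patient to be in the FAS. Suppose a share *q* of event-free patients in each arm also has no ATRS. Then

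FAS risk = r(1 − s) / [r(1 − s) + (1 − r)(1 − q)],

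which is below *r* whenever s > q. Section 2.3 implies a loss allowance of 1 − 480/530 = 9.4%. For 6% / 2% with s = 0.3, q = 5% gives 4.49% − 1.48% = 3.01 points, and q = 9.4% gives 4.70% − 1.55% = 3.15 points. The attenuation is slightly smaller but remains.

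**Effect on the choice of method.** Section 5.2.2.1 replaces the centre-adjusted model with an unadjusted interval if any expected cell is below 5. Take 177 per arm and assumed risks of 8% in one arm and 3% in each of the other two. Total events are 14.16 + 2 × 5.31 = 24.78, so the smallest expected cell is 24.78 / 3 = 8.3. With s = 0.5, 12.39 events remain and the smallest expected cell is 12.39 × 169.9 / (169.9 + 2 × 174.3) = 4.1. The lost events alone can trigger the switch.

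**The case against.** - **No strict contradiction with section 5.2.2.4.** That section is about ascertainment: an event can be fully reported and still fall outside the FAS. This is a fair reading. The fault is that the analysis set discards events the plan has taken care to record, which defeats that section's purpose.
- **The size is assumed.** This is true. The sign reversal and the inflated difference need early shares as far apart as 20% and 80%, which nothing in the SAP supports. At a 10% early share about one event is lost and the difference moves only from 4.0 to 3.6 points. The extreme rows show that the direction is not guaranteed; they are not forecasts.
- **Understatement is conditional.** It requires that early re-ruptures are lost in greater proportion than event-free patients (s > q above). The condition is plausible but should be stated.
- **Section 4.2 names only contralateral rupture** among the reasons the primary endpoint cannot be measured, which might suggest that patients with a same-side re-rupture keep answering. Section 5.1.3.2 is explicit that they do not.
- **Low weight.** Section 2.4.1 says "All other tests than described in step 1 and 2 above, will be regarded as supportive or exploratory". This limits the consequence, but it does not make the estimate right.

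**Conclusion.** The point stands. As written, the re-rupture comparison omits every re-rupture that precedes the patient's first post-baseline ATRS. This follows from the SAP's own text and needs no outside figure.

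The size depends on risks and timing that the SAP does not give. With equal early shares, the risk difference shrinks by roughly that share; with unequal shares, it can move either way. If few re-ruptures are early, the effect is small. Because few events are expected in total, even a handful lost matters to this outcome. The primary ATRS analysis, the sample size and the type I error control are not affected. It should be fixed, but it does not threaten the trial's main conclusion.

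**What to change.** In section 5.2.2.1, replace the sentence naming the FAS with wording such as:

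*Re-rupture will be analysed in every randomized patient who received treatment, in the arm assigned by randomization, whether or not any post-baseline ATRS was obtained.*

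Use this set for the 3-by-2 table, the expected-count check and whichever of the logistic or Newcombe analyses applies. It drops only the ATRS condition and fits the outcome definition in section 5.1.3.2, "a total rupture of the same Achilles tendon as treated in the trial". The set of all randomized patients already defined in section 3.3 would also remove the problem.

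Either choice brings in patients who withdrew or were lost before any ATRS. The SAP should say that they count as event-free unless a re-rupture was reported, which relies on the hospital reporting described in section 5.2.2.4. Section 4.2 should also be reconciled with section 5.1.3.2 on same-side re-rupture.

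The cost is a few lines of SAP text. Re-ruptures already reach the principal investigator independently of the questionnaires, so no new data or patients are needed.
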